Reproducibility (Short and Long Term): In order to document short term reproducibility of the imaging method and give an assessment of a meaningful change of signal in a patient, up to 10 of the subjects with COPD (from either the moderate or severe COPD groups) will undergo repeat AxV-128/Tc SPECT/CT scans within one week of the original scan. Patients will not undergo repeat imaging if there has been a significant change in their clinical status including a COPD exacerbation pulmonary infection, or CHF exacerbation. Repeat imaging will only be performed on patients with COPD as it is anticipated based upon literature documenting that never smokers have negligible levels of apoptosis within the lung. The Phase I data of AxV-128/Tc with normal subjects also demonstrated less than 5% ID lung uptake. Smokers without disease will be excluded from this reproducibility study as smoking may be variable from day to day and may alter signal results.

In addition, long term changes in this imaging method will be assessed on subjects with COPD with an additional AxV-128/Tc SPECT-CT scan and same procedures listed above. The follow up visit may be done without an additional AxV-128/Tc SPECT-CT scan and same procedures listed above. Please note that only a SUBSET of subjects will undergo 1 year or 1 week repeat scan. One year follow up visits are approximate 1 year +/- 8 months. This is to compensate for coordinating contacting participant and scheduling visits around their most convenient time.

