Imaging and data analysis: Mean \pm SD for values for uptake of AxV-128/Tc for individual lobes and for lungs will be determined for each COPD group and compared using unpaired t-test for values with Gaussian distribution and Mann-Whitney (Wilcoxon rank) test for continuous variables without normal distribution. Gaussian distribution will be determined using the Kolmogorov-Smirnov test. We have included moderate, severe and very severe COPD patients assuming that the signal will increase with the severity of COPD. We could therefore establish an exposure-response relationship between severity of COPD (on a non-linear scale) and signal. This assumption is based upon our work establishing a correlation between COPD severity and apoptotic index in the lung (12). Mean \pm SD for values for volumes and Hounsfield units will also be compared among the same groups. We will also assess tracer uptake normalized for lung volumes. In the emphysema patients we are measuring a signal coming from living (and dying) tissue that is interspersed in air. In the more severe cases of COPD, the lung tissue takes up less volume within the lungs and the air forms greater percent of each lobe. We will attempt to account for these changes by normalization for Hounsfield units. In addition values for %ID tracer uptake will be correlated with values for PA:A ratio. For the serial reproducibility studies, the values for whole lungs and lobes from the two studies will be analyzed for agreement using Bland-Altman analysis.

Incidental finding of clinical significance: Potential incidental findings of clinical significance that may be discovered during imaging procedure may include tumors, hematomas, infectious complications such as abscesses and vascular abnormalities among others.. The following procedures pertain to the finding of incidental findings (IF) that may occur during the imaging of the subjects. The images will be read by a radiologist credentialed by the Department of Radiology as soon as possible but no later than two weeks following receipt of the image. Imaging will only take place at Columbia University Medical Center. If the credentialed

radiologist will find an IF with clinical significance this will be recorded in the research record and the subject will be notified by the PI who is a critical care physician either in person or by phone followed by a letter or email.

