Serum biomarkers of inflammation and levels of apoptotic endothelial microparticles will be correlated with % injected dose of radiotracer on SPECT-CT imaging results. Up to ten patients with COPD will undergo a second SPECT-CT scan within 1 week of the first baseline/visit#1 scan in order to determine the short-term reproducibility of the signal and to determine what would be a meaningful change in signal. Patients must be clinically unchanged in the intervening week. A subset of COPD diagnosed subjects will undergo a repeat scan after 1 year of the baseline/visit#1 scan; this will include repeat SPECT-CT, pulmonary function testing, blood and urine testing. The purpose of the repeat imaging to determine (1) the ability of the initial scan to determine later lung function decline and (2) if change in signal over a 1 year time point is associated with meaningful clinical change. In addition, we will compare SPECT-CT signal (percent injected dose, %ID) as a primary endpoint, apoptotic endothelial microparticles and serum biomarkers of inflammation in patients with COPD, smoking history without COPD, and healthy non-smoking control participants. There is no human data of AxV-128/Tc SPECT-CT imaging in lung disease that would allow us to determine an appropriate sample size for this study. We will therefore base this on our rabbit studies (13) which found a %ID of approximately $0.645 +/ - 0.427\%$ in animals without and $2.0 +/ - 0.589\%$ in animals with smoke exposure with a common standard deviation of $(0.63+0.589) / 2 = 0.508\%$. We will need 5 patients per group to achieve a power of 80% and a confidence level of 99%. We will recruit 8 subjects who never smoked and are without lung disease, 8 patients who were smokers without lung disease, and 16 patients with COPD (8 with GOLD Stage 2 disease and 8 with Gold Stage 3-4 disease). Eight patients per group will give us sufficient power even when compensating for increases in variability in human subjects.

REFERENCES

1. Washko GR. Diagnostic imaging in COPD. *Semin Respir Crit Care Med.* 2010;31(3):276-85.
3. Everitt S, Hicks RJ, Ball D, Kron T, Schneider-Kolsky M, Walter T, Binns D, Mac Manus M. Imaging cellular proliferation during chemo-radiotherapy: a pilot study of serial 18F-FLT positron emission

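### Limits of agreement from at most 10 rescans are planned without a small-sample correction or confidence intervals, and the result is labelled a meaningful change when it can only show a detectable one

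*Combined protocol and SAP*

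**What the plan says.** Three places in the combined protocol and SAP bear on this.

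- **Study Protocol, Reproducibility (Short and Long Term):** "up to 10 of the subjects with COPD (from either the moderate or severe COPD groups) will undergo repeat AxV-128/Tc SPECT/CT scans" within a week of the first scan. Besides documenting reproducibility, the rescans are meant to "give an assessment of a meaningful change of signal in a patient". Patients with a significant clinical change in between are not rescanned.
- **Study Protocol, Imaging and data analysis:** for these serial studies, "the values for whole lungs and lobes from the two studies will be analyzed for agreement using Bland-Altman analysis". No other analysis of the one-week pairs is named.
- **Statistical Procedures:** the maximum of ten is repeated, and the second scan is there to "determine the short-term reproducibility of the signal and to determine what would be a meaningful change in signal". It adds: "Patients must be clinically unchanged in the intervening week".

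Statistical Procedures also plans a repeat scan at one year in a subset of COPD patients. One of its two aims is to see whether signal change over that year goes with clinically important change. The size of the subset, the clinical measure and the method are not given.

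The documents do not state a multiplier or nominal coverage for the limits, a small-sample adjustment, confidence intervals for the limits, or a reason for choosing 10 pairs.

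**The concern.** There are two issues, one of precision and one of labelling.

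**Precision.** The usual Bland-Altman limits apply a normal multiplier to an estimated mean and SD as if both were known. That does little harm with many pairs. With 10 or fewer, the limits are on average too narrow for judging the next patient, and they vary a good deal from one study to another. If only two limits are reported, the reader cannot see this.

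**Labelling.** The rescanned patients are required to be stable, so their differences contain only test-retest variation. That variation shows how large a change must be to exceed noise. It cannot show that a change of that size matters to a patient.

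What is at stake is how the repeatability result will be read and reused. The Scientific Abstract hopes the probe may eventually help to monitor response to therapy. Anyone who takes published limits from this study for that purpose would be using limits that are too narrow on average and carry a label the data do not support.

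**Working it through.** The documents give no coverage or precision figure for this sub-study, so there is nothing of the plan's own to reproduce.

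**Inputs**

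- Number of pairs: n ≤ 10 (Reproducibility; Statistical Procedures). Because 10 is a maximum, n = 8 and n = 6 are shown too.
- Multiplier: not stated. Assumed to be the conventional 1.96 (nominal 95%), with variants below.
- Differences assumed normal with constant variance.

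**Formulas**, with SD the sample SD of the differences and T a Student t variable on n − 1 degrees of freedom

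1. Expected coverage of mean ± 1.96 SD for one new stable patient: P(|T| < 1.96 / √(1 + 1/n)).
2. Multiplier that gives 95% expected coverage: t(n−1, 0.975) × √(1 + 1/n).
3. 95% half-width of each conventional limit, in SD units: t(n−1, 0.975) × √(1/n + 1.96² / (2(n − 1))).

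**At n = 10**

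1. 1.96 / √1.1 = 1.869. On 9 degrees of freedom the coverage is 90.6%. A simulation of one million samples of 10 pairs agrees (90.55%).
2. 2.262 × √1.1 = 2.373, and 2.373 / 1.96 = 1.21, so the limits become about 21% wider.
3. 2.262 × √(0.1 + 3.8416/18) = 2.262 × 0.560 = 1.27 SD.

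| Pairs | Expected coverage of ± 1.96 SD | Multiplier for 95% | 95% half-width of each limit |
|---|---|---|---|
| 10 | 90.6% | 2.37 | 1.27 SD |
| 8 | 89.3% | 2.51 | 1.49 SD |
| 6 | 87.1% | 2.78 | 1.91 SD |

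**Sensitivity to the assumption, n = 10.** A multiplier of 2 gives 91.1%. Fixing the mean difference at zero gives 91.8% (SD on 9 degrees of freedom) or 92.2% (10 degrees of freedom). None of these reaches 95%.

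**Spread between studies, n = 10.** The figures above are averages. In the same simulation the true coverage of one study's limits ran from about 74% to 99% (5th to 95th percentile) and was below 95% in 63% of samples. The 95% confidence interval for the SD runs from 0.69 to 1.83 times its estimate. This uncertainty is a larger problem than the average shortfall of about 4 points, and it is the reason to report confidence intervals.

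**The case against.** The best defence is that the plan commits to less than the calculation assumes. It names a method suited to agreement data and leaves the details open. It does not state 1.96 or 95%, and it does not rule out confidence intervals. It also distinguishes a meaningful change in signal, taken from the one-week scans, from clinically meaningful change, examined at one year. The first can fairly be read as change beyond measurement noise, which is what test-retest data provide. And this is a sub-study of at most 10 pairs in a first use of the tracer in lung disease.

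Much of that stands. The multiplier is an assumption, and the labelling issue is mainly one of clarity. It remains that a section which sets the size of a change from so few pairs should state its limits and their uncertainty, and that the word meaningful invites a clinical reading.

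Two stronger readings are tempting but lack support.

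- *A reader might infer that the one-week limits serve as a cut-off for calling one-year changes real.* No section defines a cut-off, classifies a patient as changed, or applies the one-week limits to the one-year scans. The one-year aim is an association. The coverage shortfall is therefore not an error rate of any decision rule in the plan.
- *A reader might infer that lobes from one patient are pooled as independent pairs.* The plan mentions whole lungs and lobes but nowhere says lobes are pooled, and separate analyses are the natural reading. Pooling would make the standard error of the mean difference too small, but the limits depend mainly on the SD. A simulation of 10 patients with 5 lobes each, with common lobe mean and variance and an assumed within-patient correlation of 0.3 to 0.7, gave coverage for a new lobe difference of 93.4% to 91.6%, no worse than whole-lung limits at n = 10.

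**Conclusion.** The point holds as an inexpensive improvement to a secondary sub-study. If conventional limits are used, they will cover on average about 91% of new stable patients at the maximum of 10 pairs, and less with fewer. Each limit will be uncertain by about 1.27 SD either way. This rests on an assumed 1.96 multiplier and on normal differences of constant variance; the variants tried move the n = 10 figure only to between 91.1% and 92.2%.

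The label should change because the rescans come from stable patients, and because clinical relevance already has its own place in the one-year aim. It would go too far to say that the plan claims the one-week result proves clinical relevance. The comparison of percent injected dose between groups, which is the primary endpoint, is not touched.

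**What to change.** 1. In **Imaging and data analysis**, specify limits for the whole-lung values as mean difference ± t(n−1, 0.975) × √(1 + 1/n) × SD, with n the number of pairs obtained (2.37 SD at n = 10), and report 95% confidence intervals for the limits of agreement. The t-based multiplier corrects coverage only on average; the intervals show how uncertain the limits remain.
2. In **Reproducibility (Short and Long Term)** and **Statistical Procedures**, call the one-week result the smallest detectable change, meaning change beyond test-retest noise, and say that clinical meaning will be judged from the one-year association already planned.

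No extra scans, patients or radiation are needed. The price is limits about 21% wider at n = 10, and more with fewer pairs.

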
Study Design:

This will be a prospective study examining the use of ^{99m}Tc -Annexin V-128 (AxV-128/Tc) SPECT/CT technology in the imaging and functional assessment of the lung of patients with COPD, healthy volunteer smokers without COPD and healthy volunteer subjects without smoking history.

STUDY PROTOCOL

We will study patients with and without lung disease (COPD) and compare AxV-128/Tc SPECT-CT scans. To test the hypothesis that AxV-128/Tc SPECT-CT scanning can detect apoptosis in patients with COPD, we will perform a case control study in patients with varying severity of COPD. There will be four groups of subjects: -Patients with moderate COPD: GOLD Stage II, $\text{FEV}_1/\text{FVC} < 0.7$ and $\text{FEV}_1 < 50\%$ predicted -Patients with severe COPD: GOLD Stage III-IV, $\text{FEV}_1/\text{FVC} < 0.7$ and $\text{FEV}_1 < 50\%$ predicted -Healthy controls who are currently smoking (> 10 pack years) with normal spirometry ($\text{FEV}_1 > 80\%$ and $\text{FEV}_1/\text{FVC} > 70\%$) - Healthy controls who never smoked (less than 100 lifetime cigarettes) with normal spirometry ($\text{FEV}_1 > 80\%$ and $\text{FEV}_1/\text{FVC} > 70\%$) The subjects will undergo spirometry (lung function tests) and blood and urine samples will be drawn prior to undergoing SPECT Scan. The spirometry will ascertain the severity of COPD and blood and urine samples will allow us to measure markers of lung injury as well as cotinine to confirm the smoking status of the subject. Blood samples will be also stored for analysis of biomarkers and possible future DNA and RNA analysis.

Study population: We will study 16 patients with COPD (8 patients with GOLD Stage 2 disease, 8 patients with GOLD Stage 3-4 disease) and 8 healthy volunteer smokers without COPD, and 8 healthy volunteer subjects without smoking history or lung disease to compare AxV-128/Tc SPECT-CT scans in smokers, patients with COPD, and normal control patients.

Recruitment: The patient population will be drawn from the Center for LAM and Rare Lung Diseases, Jo-Ann F. LeBuhn Center for Chest Disease and the Price Family Center for Comprehensive Chest Care and will be stratified by severity of disease. Recruitment of healthy volunteers will be performed with advertisements in Columbia University's "recruitme" website, and flyers throughout the medical center. In order to be eligible, patients with COPD must have a

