If an IF has been reported we will notify the IRB during the next review about the number of Required Review Images, a list of the subject study numbers, the type of scan, the date of the scan, a description of the IF of Clinical Significance, the date of communication with the subject and the outcome, if known.

Eligibility Criteria

Inclusion Criteria:

1. Males and females age 45-80 years
2. Able and willing to comply with the study procedures
3. Gold class II COPD or greater
4. Healthy Smoker
5. Healthy non-smoker
6. Lie flat for 30 minutes

Exclusion Criteria:

1. Current Malignancy
2. Bronchiectasis
3. Recent COPD exacerbation (less than 1 month)
4. Recent pulmonary infection (less than 1 month)
5. Asthma or other significant lung disease
6. Pregnancy or lactation
7. Claustrophobia or inability to lie still in a supine position

RESEARCH AIMS & ABSTRACTS

Research Question(s)/Hypothesis(es):

We hypothesize that there will be an increased AxV-128/Tc signal in the lungs of patients with COPD as compared to control patients. This signal is hypothesized to be higher in patients with more severe COPD.

Scientific Abstract:

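### The case-control comparison neither matches nor adjusts for age or sex, so an imbalance between COPD patients and controls could be read as a COPD effect on tracer uptake

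*Combined protocol and SAP*

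**What the plan says.** All references are to the combined protocol and SAP.

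- **Design (Study Protocol).** To test the imaging hypothesis, "we will perform a case control study in patients with varying severity of COPD". There are four groups of 8: GOLD 2, GOLD 3-4, current smokers with normal spirometry, and never-smokers with normal spirometry. Spirometry and smoking history define the groups; age and sex do not.
- **Eligibility Criteria.** One list covers everyone, and its only demographic rule is "Males and females age 45-80 years".
- **Recruitment.** Patients come from specialist chest centers and "will be stratified by severity of disease". Healthy volunteers come through a university recruitment website and "flyers throughout the medical center".
- **Imaging and data analysis.** Uptake is summarised for each COPD group and "compared using unpaired t-test for values with Gaussian distribution and Mann-Whitney (Wilcoxon rank) test for continuous variables without normal distribution". Uptake normalised for lung volume will also be assessed. For the greater share of air in severe disease, the section says "We will attempt to account for these changes by normalization for Hounsfield units".
- **Statistical Procedures.** %ID is the primary endpoint, to be compared with the biomarkers across COPD patients, smokers without COPD and non-smokers. No test is named for that comparison.

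**The concern.** Without randomisation, groups are made comparable either at recruitment or in the analysis. Here the stratification is by disease severity, which cannot balance cases against controls, and the two arms of the main contrast reach the study by different routes. Clinic patients and volunteers answering an advertisement may differ in age and sex mix, and a 35-year age span leaves room for that. With 8 per group, chance adds to it.

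If age or sex influences uptake, C-reactive protein, fibrinogen or microparticle counts, the difference between groups contains that influence, and nothing in the plan would separate it from disease. If COPD patients are older and uptake rises with age, the error favours the study's hypothesis.

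**Working it through.** **1. The plan's own figure.** Statistical Procedures gives rabbit %ID of 0.645 (SD 0.427) without smoke exposure and 2.0 (SD 0.589) with it. The difference is 2.0 - 0.645 = 1.355. The common SD used is 0.508, which is (0.427 + 0.589)/2; the sum printed there uses 0.63 in place of 0.427, a separate slip. The standardised difference is 1.355/0.508 = 2.67. At alpha 0.01 and 80% power, a t-test needs 5 per group one-sided or 6 two-sided (two-sided power at 5 per group is 77.3%). The stated 5 is therefore reproduced closely and is not in dispute. The calculation makes no allowance for confounding.

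**2. Assumed bias.** The documents give no relation between age or sex and uptake, so these inputs are assumptions:

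- slope of uptake on age: 0, or 0.2 to 0.5 SD per decade;
- age gap, COPD minus controls: 0, or 8 to 12 years.

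Bias in SD units = slope × gap/10. The range is 0 (no slope or no gap), then 0.2 × 0.8 = 0.16 up to 0.5 × 1.2 = 0.60. In %ID this is 0.16 × 0.508 = 0.08 to 0.60 × 0.508 = 0.30. Against the planning difference it is 0.081/1.355 = 6% to 0.305/1.355 = 22%.

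**3. Error rate of an unadjusted t-test when COPD has no effect.** The test statistic is noncentral t with n1 + n2 - 2 degrees of freedom and noncentrality shift/√(1/n1 + 1/n2). For example, 0.60 SD at 16 versus 8 gives 0.60/√(1/16 + 1/8) = 1.39. The plan states 99% confidence without saying whether tests are one- or two-sided; two-sided is assumed here.

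| Shift (SD) | 16 vs 8, 1% | 8 vs 8, 1% | 16 vs 8, 5% | 8 vs 8, 5% |
|---|---|---|---|---|
| 0 | 1.0% | 1.0% | 5.0% | 5.0% |
| 0.16 | 1.5% | 1.3% | 6.4% | 6.0% |
| 0.36 | 3.6% | 2.7% | 12.5% | 10.3% |
| 0.60 | 9.8% | 6.6% | 26.3% | 20.1% |

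More subjects would not help. At the 5% level a 0.5 SD shift gives 15.4% at 8 versus 8 and 27.8% at 16 versus 16.

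**4. Sex imbalance by chance.** If both sources were half men, two independent binomial(8, 0.5) counts would differ by 3 or more with probability 21%.

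**5. What adjustment buys and costs.** In simulation at 8 versus 8, a linear model with group, age and sex held the 5% test at 4.5-5.1%, while the unadjusted test rose to 8.9-28.3% (within-group age-uptake correlation 0.3-0.5, age gap 1-1.5 SD).

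For power, let g be the age gap in within-group age SDs. The variance of the group effect is multiplied by 1 + g²/4, and 16 - 4 = 12 degrees of freedom remain. With the residual SD taken as unchanged, power at two-sided 1% for 1.355 %ID is:

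| | Unadjusted | Adjusted, g = 0 | g = 1 | g = 2 |
|---|---|---|---|---|
| SD 0.508 | 98.2% | 97.6% | 93.4% | 74.8% |
| SD 0.762 (1.5 times larger) | 71.1% | 68.6% | 56.6% | 34.4% |

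**The case against.** The strongest reply is that the bias is hypothetical. No age slope appears in the documents. The Scientific Abstract says apoptosis is absent from the normal adult lung, and the reproducibility section expects negligible levels in never-smokers. On that premise a steep age slope in never-smokers is not expected. This stands as a reason to include zero in the range. It does not settle the matter, because non-specific uptake could vary with age and the plan itself says there are no human data in lung disease.

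Other points also stand in part:

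- **Lung size.** Normalisation for lung volume partly covers the route by which sex could affect whole-lung uptake. It is an additional analysis, though; the primary endpoint remains plain %ID, and nothing addresses age.
- **Error level.** The plan's stated level is 99% confidence, so the 1% columns are the relevant ones. The 5% columns are for reference only.
- **Named test.** The unpaired tests are tied to the COPD groups. That COPD versus controls will be tested unadjusted is an inference from silence, but no adjusted method appears anywhere.
- **Scope.** The different recruitment routes affect COPD versus controls. Moderate and severe patients come from the same clinics, so that argument does not reach the severity comparison.

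A reader might infer that the design will produce a false COPD effect, or that controls in their late 40s will face patients in their 70s. The documents support neither: the age floor of 45 is shared, no expected age distribution is given, and no effect of age on uptake is shown.

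**Conclusion.** The gap is real: the primary contrast is non-randomised, draws cases and controls from different sources, and has no matching, covariate model or sensitivity analysis for age or sex. The bias this could cause is unknown and may be zero; the 1.5-9.8% and 1.3-6.6% figures rest wholly on the assumed slope and age gap, and on the rabbit SD for their %ID equivalents.

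Even at the top of the assumed range, the bias is under a quarter of the planning difference, so it could not account for an effect of the rabbit size. It becomes important if the human effect is smaller, and the same lack of control applies to the biomarker comparisons. This is an inexpensive improvement that should be made, not a fatal flaw.

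**What to change.** 1. Keep the 45-80 range. Frequency-match each control group to the COPD groups on sex and broad age band (for example 45-59, 60-69 and 70-80), enrolling COPD patients first or in parallel so that the target mix is known.
2. Tabulate age and sex by group.
3. Name the COPD-versus-control comparison of %ID, and report beside it a pre-specified supporting linear model of %ID on group, age and sex.

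If enrolment is too far advanced for matching, items 2 and 3 can still be added.

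**Cost.** No extra subjects or procedures, but slower recruitment of older healthy smokers and two degrees of freedom in the adjusted model. If matching is poor, the adjusted estimate also loses appreciable power: about 75% against 98% at a 2-SD age gap. That is why balance at recruitment should come first, with the model as support.
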